Interventions such as acupressure, massage, and art or music therapy fall under the CAM category (Chen & Tang, 2020; Rau et al., 2023; Zick et al., 2021). Considering the specific characteristics of leukemia and the need for practical clinical application, music therapy presents as a non-invasive, safe, comfortable, and easily administered nursing intervention. It can be conveniently implemented by healthcare providers, patients themselves, or family members. Research indicates that music therapy can reduce depression, anxiety, and pain in cancer patients (Köhler et al., 2020; Li et al., 2020; SezgiN & Bektas, 2022). Unfortunately, the application of music therapy for managing CRF in leukemia patients remains limited. Therefore, this study aims to investigate the effects of music therapy on fatigue and clinical laboratory values (e.g.,

White Blood Cell [WBC] count, Hemoglobin [Hb], Albumin) in patients with acute leukemia, to provide a reference for clinical practice.

Section 1: Research Purpose

To investigate the effects of music therapy on fatigue and clinical laboratory values (White Blood Cell count, Hemoglobin, and Albumin) in patients with acute leukemia.

Section 2: Research Hypotheses

1. Patients with acute leukemia who receive music therapy will experience lower levels of fatigue during chemotherapy compared to those receiving standard care.
2. Patients with acute leukemia who receive music therapy will demonstrate improved clinical laboratory values (White Blood Cell count, Hemoglobin, and Albumin) during chemotherapy compared to those receiving standard care.

Literature Review

I. Leukemia and Its Classification

According to the Global Cancer Observatory (GLOBOCAN) (2020), the global incidence of leukemia was 5.4 per 100,000 population, with a mortality rate of 3.3 per 100,000 population (Sung et al., 2021). In Taiwan, statistics from the Ministry of Health and Welfare (2022) indicate that malignant neoplasms have remained the leading cause of death for the past four decades. Leukemia ranked 13th among cancer deaths, with an incidence rate of 2.9 per 100,000 and a mortality rate of 5.0 per 100,000.

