moderate positive correlation between WBC count and fatigue ($r = 0.63$, $p < 0.05$). However, other studies, including those on post-operative colorectal cancer patients and leukemia patients, reported no significant correlation between fatigue severity and WBC count ($\beta = -0.037$, $p = 0.588$; $\beta = 0.16$, $p = 0.29$, respectively) (Addisia et al., 2022; Wei & Li, 2018).

The possible reasons for these discrepant findings may relate to cancer type and stage. Different cancer types and stages necessitate different treatment dosages, leading to varying degrees of myelosuppression (Anand et al., 2023; Kuter, 2015). Furthermore, the timing of fatigue assessment is relevant. If assessed during chemotherapy, patients are likely experiencing side effects, including leukopenia. If survivors are assessed, the decrease in WBCs may be less pronounced. The week following chemotherapy is the period of peak side effects (Chen & Tang, 2020). Therefore, research designs should collect blood laboratory values concurrently with fatigue assessments during the patient's chemotherapy process to accurately monitor the fatigue problem. Study designs must reflect the clinical reality, synchronizing the collection of laboratory data and fatigue assessments to effectively capture the correlation between fatigue and WBC count.

2. Hemoglobin (Hb) According to the World Health Organization (WHO) and the American Association of Blood Banks (AABB), anemia is defined as $Hb < 12$ g/dl for females and < 13 g/dl for males (Lotterman & Sharma, 2022; Safiri et al., 2021). Anemia ($Hb < 12$ g/dl) can result from the cancer itself, treatments (chemo/radiotherapy), malnutrition, bone marrow infiltration, or hemorrhage (Madeddu et al., 2018; Wang et al., 2002). Chemotherapy side effects cause myelosuppression, inhibiting erythropoiesis (red blood cell production) (Jhamb et al., 2008; Thong et al., 2020). This leads to insufficient hemoglobin, which impairs systemic oxygen delivery and subsequently causes fatigue (Thong et al., 2020; Wang, 2008). While 0% to 67% of chemotherapy patients may develop anemia, some studies note that fatigue can occur even in non-anemic cancer patients (Gaston-Johansson et al., 1999).

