Based on the literature review, CRF is a significant and distressing problem for leukemia patients. Due to the disease itself, considerations for hemoglobin, platelets, and patient activity safety severely limit the available intervention options for fatigue. Music therapy is a non-invasive, safe, comfortable, and easily administered nursing intervention. Following appropriate assessment and selection of resonant music based on client preferences, it can be implemented by healthcare providers or by the patients' families.

Discrepancies exist between domestic (Taiwanese) and international music therapy practices, primarily in education systems, professional certification, legal regulations, and cultural factors. Currently, Taiwan lacks a formal certification system for music

therapists, unlike many other countries. Compounded by financial constraints that often preclude hiring therapists with foreign qualifications, the implementation of standardized MT is challenging.

Therefore, this study aims to recruit patients newly diagnosed with leukemia who are undergoing conventional chemotherapy. It will utilize music therapy as an intervention to investigate its effects on fatigue and clinical laboratory values.

Research Methods

This chapter is divided into nine sections, detailing the methods and procedures of this study. It includes: (1) research framework, (2) research design, (3) research setting and participants, (4) sample size, (5) the music therapy protocol, (6) research instruments and reliability/validity, (7) research procedures, (8) ethical considerations, and (9) data processing and analysis.

Research Framework

Based on the aforementioned literature review, the research framework for this study was developed as illustrated in Figure 3-1.

The primary purpose of this study is to investigate the effects of music therapy on fatigue and clinical laboratory values (e.g., White Blood Cell [WBC] count, Hemoglobin [Hb], Albumin) in patients with acute leukemia undergoing chemotherapy. The study is designed to provide music therapy to this patient population, utilizing fatigue severity and clinical laboratory values as the primary outcome variables. This framework will be used to compare the differences in these key outcome variables between the music therapy group and the standard care group.

Research Design

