This study employs an **experimental research design** utilizing **randomized assignment** and **repeated measures**. Participants who consent to the study will be allocated to either the experimental group (Group A) or the control group (Group B). Group A participants will listen to self-selected music in addition to receiving standard care. Group B participants will receive standard care only. The objective is to evaluate the effectiveness of music therapy in alleviating fatigue. A total of 44 patients with leukemia undergoing their initial chemotherapy will be recruited, with 22 participants allocated to each group.

The measurement process will be conducted in two parts:

1. **Primary Data Collection:** Data will be collected at two main time points: upon admission for initial chemotherapy (Baseline, T0) and on Day 21 of the

chemotherapy cycle (T1). On Day 21, the researcher will visit the ward to collect the required data, including the Tang's Fatigue Scale, the Fatigue Numerical Rating Scale (NRS), and clinical laboratory data. If a participant has been discharged, data will be collected via telephone interview or an online questionnaire.

2. **Symptom Diary:** Participants will record their fatigue levels using the Fatigue NRS immediately following each music therapy session.

Baseline demographic data will be collected only at T0. The measurement time points and the application of corresponding instruments are detailed in Table 3-2.

Table 1: Schedule of Research Measurements

Time	Before Chemo (T0)	Chemo Day 7	Chemo Day 14	Chemo Day 21 (T1)
Tang's Fatigue Scale	○			○
Numerical Rating Scale (NRS)	○	○	○	○
WBC	○			○
Hemoglobin	○			○
Albumin	○			○
Demographic Data	○			

Note: ○ = Data to be collected

Research Setting and Participants

This study will be conducted in the hematology-oncology ward of a medical center located in Northern Taiwan. Participants must meet the following inclusion criteria:

1. Clinically diagnosed with Acute Myeloid Leukemia (AML) by a specialist physician.
2. Scheduled to receive initial (first-time) chemotherapy.
3. Aged 20 years or older.
4. Able to communicate in Mandarin or Taiwanese.
5. Possess normal hearing ability.
6. No history of psychiatric illness and clear consciousness.
7. No prior participation in any fatigue management intervention study.
8. Understands the research purpose, voluntarily agrees to participate, and has signed the informed consent form.

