9. Willing to cooperate with all study procedures during the research period.

Participants will be **excluded** from the study if they meet the following criteria:

1. Severe hearing impairment.

2. Unstable vital signs or unclear consciousness.

III: Sample Size Calculation

The sample size was estimated based on the **Generalized Estimating Equations (GEE)** approach for repeated measures. The analysis will control for baseline demographic and disease characteristics as covariates (e.g., age, sex, education level, occupation, perceived economic status, marital status, religious beliefs, and metastasis). The dependent variables are fatigue, White Blood Cell (WBC) count, hemoglobin, and albumin.

The calculation was performed using G*Power software (version 3.1.9.7). Parameters were set as follows: a significance level (α) of 0.05, statistical power ($1-\beta$) of 0.80, a 95% confidence interval, and an anticipated **effect size of 0.21**. This calculation yielded a required sample size of 34 participants (as shown in Figure 3-2). To account for a potential attrition rate of 30%, the study aims to recruit a total of **44 participants** ($n=22$ for Group A, $n=22$ for Group B).

Music Therapy Protocol

1. Music Selection, Dosage, and Headphone Use

According to the literature, a music therapy duration of 15–30 minutes is effective for fatigue alleviation (Burns et al., 2008; Cassileth et al., 2003; Miladinia et al., 2021; Reimnitz et al., 2020; Sezgin & Bektas, 2022). Music selection will be based on individual preferences and cultural background (Tsai & Chou, 2015; Browning, 2000; Gerdner, 2000).

To ensure data integrity while considering the patient's length of stay, physical burden during chemotherapy, and protocol adherence, the music therapy intervention in this study will be administered **once daily for 21 consecutive days**. The **30-minute intervention** will commence at the start of the chemotherapy infusion. During the study, participants will be provided with a chemotherapy symptom tracking diary to confirm adherence to the music therapy protocol in the experimental group.

For reasons of personal hygiene, preference, and potential patient discharge, participants will be asked to use their own headphones. If a participant does not have headphones, a set will be provided by the researcher.

Research Instruments and Psychometric Properties

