1. Participant Demographic Data Sheet Data will be collected using Google Forms or paper questionnaires, as appropriate. This sheet includes demographic information such as age, sex, education level, occupation, perceived economic status, marital status, and religious beliefs, to be completed by the participant. The questionnaire also

includes items regarding the participant's prior musical training, frequency of daily music listening, motivations for listening, typical timing and methods of listening, and preferred activities during rest.

2. Leukemia-Related Treatment Data Sheet This data will be extracted from the patient's medical records by the researcher. It includes information on chemotherapy drugs and dosages, as well as laboratory values—specifically Absolute Neutrophil Count (ANC), Hemoglobin (Hb), and Albumin—from before chemotherapy (T0) and on Day 21 (T1).

3. Tang Fatigue Rating Scale (TFRS) While many reliable and valid fatigue scales exist globally, many have limitations. Considering that fatigue assessment should encompass physical, psychological, and activity dimensions, the TFRS was selected as the primary outcome measure for this study.

The TFRS contains 37 items across three subscales: Physical (15 items), Psychosocial (12 items), and Daily-Living (10 items). It uses a 10-point rating scale, where higher scores indicate greater fatigue severity. The TFRS underwent content validity testing by three PhD-level experts in fatigue theory and psychometrics. It was validated in a sample of 107 patients with chronic heart failure. The internal consistency (Cronbach's α) was 0.96 for the total scale, and 0.83 (Physical), 0.92 (Psychosocial), and 0.97 (Daily-Living) for the subscales. The TFRS demonstrated excellent validity: **convergent validity** with the Visual Analogue Scale for Fatigue (VAS-F) was 0.87, and **construct validity** with The Beck Depression Inventory-Second Edition (BDI-II) was 0.77 (Tang et al., 2010).

In the study by Tang et al. (2010), the TFRS also showed a significant positive correlation with the New York Heart Association (NYHA) functional class ($r = 0.75, p < 0.01$) and significant negative correlations with Ejection Fraction (EF) ($r = -0.46, p < 0.01$) and Hemoglobin (Hb) ($r = -0.27, p < 0.01$) (Tang et al., 2010).

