will be categorized into four measurement scales: nominal, ordinal, interval, and ratio (Kaur et al., 2018). Nominal and ordinal scale data are considered **categorical variables** (e.g., sex, education level, occupation, perceived economic status, marital status, religious beliefs, and chemotherapy drug names) and will be presented as frequencies (n) and percentages (%). Interval and ratio scale data are considered **continuous variables** (e.g., age, fatigue severity, Absolute Neutrophil Count [ANC], hemoglobin, and albumin) and will be presented using means, standard deviations (SD), and ranges (minimum and maximum) (Kaur et al., 2018).

- **b. Inferential Statistics:** This study utilizes an experimental design with longitudinal follow-up and repeated measures, analyzed on an **intention-to-treat (ITT)** basis. It will compare the differences in fatigue severity and clinical laboratory values between the music therapy and control groups. During the study, data attrition may occur due to factors such as disease progression or a participant's personal decision to withdraw, leading to unequal sample sizes at different measurement points. Therefore, this study will employ **Generalized Estimating Equations (GEE)** to analyze the relationship between the independent and dependent variables. GEE will be used to compare pre- and post-test values (fatigue severity, Absolute Neutrophil Count [ANC], hemoglobin, and albumin) between the experimental and control groups. A *p*-value of < 0.05 will be considered the standard for statistical significance (Ziegler & Vens, 2010).

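### The white-cell outcome is WBC in hypothesis 2 and the measurement schedule, but ANC on the data sheet and in the GEE list; the fatigue measure in that list also needs naming

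*Combined protocol and SAP*

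**What the plan says.** White-cell outcome. Hypothesis 2 reads: "Patients with acute leukemia who receive music therapy will demonstrate improved clinical laboratory values (White Blood Cell count, Hemoglobin, and Albumin) during chemotherapy". The Sample Size Calculation section says: "The dependent variables are fatigue, White Blood Cell (WBC) count, hemoglobin, and albumin". The table headed "Table 1: Schedule of Research Measurements" has a WBC row at T0 and Day 21 and no ANC row. The Research Framework names WBC among the laboratory values, and Research Procedures lists WBC among the values to be taken from medical records. The literature review argues for WBC as well, calling for "synchronizing the collection of laboratory data and fatigue assessments to effectively capture the correlation between fatigue and WBC count".

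Two operative places differ. The treatment data sheet (Research Instruments, item 2) lists the laboratory values as "specifically Absolute Neutrophil Count (ANC), Hemoglobin (Hb), and Albumin". The inferential statistics paragraph says: "GEE will be used to compare pre- and post-test values (fatigue severity, Absolute Neutrophil Count [ANC], hemoglobin, and albumin". The descriptive statistics paragraph also gives ANC, but as an example.

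Fatigue and primary status. The Research Framework describes the study as "utilizing fatigue severity and clinical laboratory values as the primary outcome variables". Research Instruments, item 3, says "the TFRS was selected as the primary outcome measure for this study". The inferential paragraph names neither the TFRS nor the NRS; it refers only to the severity of fatigue.

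**The concern.** WBC and ANC are different quantities: ANC counts one component of the white cells. The data sheet decides what is extracted and the GEE sentence decides what is tested. If staff work from those two places, the white-cell result will be for ANC, while hypothesis 2 is about WBC. Either variable could later be presented as the planned one with support in the text, and a reader could not tell a planned result from a chosen one.

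The fatigue wording raises a smaller question of the same kind. The plan describes both the TFRS and the NRS as measuring how severe fatigue is, and Table 1 schedules both at T0 and Day 21. The analysis paragraph does not say which it means, nor whether the laboratory values share primary status with fatigue.

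**Working it through.** The main check is textual.

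**White-cell variable, place by place**

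- Research Purpose and hypothesis 2: WBC.
- Research Framework: WBC (introduced as an example).
- Table 1, T0 and Day 21: WBC; no ANC row.
- Sample Size Calculation, dependent variables: WBC.
- Research Procedures, record review: WBC.
- Research Instruments, item 2, data sheet: ANC; no WBC. The wording is specific.
- Descriptive statistics list: ANC, as an example only.
- GEE list: ANC; no WBC. It is not worded as a list of examples.

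So WBC is in neither analysis list, and ANC is in no hypothesis, schedule or dependent-variable list. The firm evidence for ANC is the data sheet and the GEE sentence. The conflict is in running prose, so a broken table or removed text does not explain it.

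**Fatigue measure**

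Item 3 of Research Instruments ties the TFRS to primary status. Items 3 and 5 each describe their scale's scores in terms of fatigue severity. The post-test set in Research Procedures contains both scales. The GEE sentence therefore fits either one.

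**The plan's own figure**

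The point disputes no number. The one computed figure that depends on the outcome schedule is the required 34 participants. The plan gives effect size 0.21, α 0.05 and power 0.80. It does not give the number of measurements m, the correlation ρ or the effect-size metric. Assume Cohen's f, two groups, ρ = 0.5 and the G*Power within-between interaction test:

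λ = f² × N × m / (1 − ρ), df1 = m − 1, df2 = (N − 2)(m − 1)

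- m = 4: λ = 0.0441 × 34 × 4 / 0.5 = 12.0, df 3 and 96, power 0.823. The smallest even N reaching 0.80 is 34, the plan's figure.
- m = 2: λ = 0.0441 × 34 × 2 / 0.5 = 6.0, df 1 and 32, power 0.66. The N needed is 48, and runs from 66 to 30 as ρ goes from 0.3 to 0.7.

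In Table 1 the NRS has four time points, and the TFRS and laboratory values have two. This suggests, but does not prove, that the sample size was worked out on the NRS schedule: m = 3 with ρ = 0.6 gives 32, which is also close.

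**Illustrative error rates (hypothetical)**

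- Better of two two-sided tests at 0.05: 1 − P(|Z1| < 1.96 and |Z2| < 1.96), with (Z1, Z2) bivariate normal. This is 0.0951 at correlation 0.3, 0.0835 at 0.7 and 0.0704 at 0.9.
- Any of four independent tests at 0.05: 1 − 0.95⁴ = 0.1855.

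The first needs a WBC/ANC (or TFRS/NRS) correlation and a habit of reporting the better result. The second needs independence and a rule that any one significant result is success. The plan gives none of these.

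**The case against.** Three stronger readings are tempting, and the documents do not support them.

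A reader might infer that the white-cell part of hypothesis 2 has no planned test at all. That goes too far. The Sample Size Calculation section describes the GEE analysis and lists WBC as a dependent variable, Research Procedures requires WBC to be extracted, and the inferential paragraph promises a comparison of laboratory values, which the hypotheses define to include WBC. Passages conflict; an analysis is not absent.

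A reader might infer that the two statements about the primary outcome flatly contradict each other. The TFRS sentence comes in a passage on choosing among fatigue scales. It can be read as picking the instrument for the fatigue part of the framework's primary outcomes, with the laboratory values still primary beside it. What stands is that item 3 names only the TFRS and leaves the status of the laboratory values unsaid. Table 3-3, which the analysis section cites as its outline, is not in the available text and may name the instrument or a testing order. It could not remove the WBC/ANC conflict from the prose.

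A reader might infer an inflated false-positive rate. The GEE sentence names one white-cell variable, not a choice of two, and no any-one-wins rule is stated. The percentages above illustrate what loose definitions can permit; they are not properties of this plan.

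**Conclusion.** The white-cell contradiction holds with high confidence and needs correcting. Its extent is one of the three laboratory components of hypothesis 2: the data sheet and the GEE sentence, taken literally, would deliver ANC where the hypothesis, schedule and dependent-variable list call for WBC. This rests on the text alone and needs no assumption.

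The fatigue and primary-status point holds with moderate confidence, as an ambiguity to clear up and not as a firm contradiction. It depends partly on what Table 3-3 says. No error rate should be attached to either part.

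**What to change.** Replace ANC with WBC on the treatment data sheet and in both the descriptive and GEE lists. Keep ANC, if wanted, only as a separately labelled exploratory variable. If ANC is in fact intended, amend the purpose and hypothesis 2, the framework, Table 1, the dependent-variable list and the record-review text instead. Date that amendment before outcome data are examined by group.

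In the inferential paragraph, name the TFRS as the primary fatigue outcome, as Research Instruments already does, and list the NRS as secondary. State whether WBC, hemoglobin and albumin are primary or secondary. If they stay primary, say how the several results lead to a conclusion; the method is a trade-off for the sponsor. Make Table 3-3 agree.

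The cost is wording plus one extraction field. WBC at T0 and Day 21 is already scheduled and taken from records of routine care, so no extra blood draw is needed. Naming the TFRS does call for a check on which measurement schedule the 34 was based, since under the assumptions above a two-time-point outcome has power of about 0.66 at that size.

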Prior to study commencement, approval will be obtained from the Institutional Review Board (IRB). Following IRB approval, and after explaining the study to and receiving consent from the attending physicians and ward nursing staff, the researcher will conduct participant recruitment in the inpatient wards and outpatient clinics. Individuals who meet the inclusion criteria will be identified as potential participants. The researcher will explain the study's purpose and methodology to these individuals. After obtaining informed consent and a signed consent form, the researcher will administer the pre-test (T0) questionnaires. This packet includes the Demographic Data Sheet, the Tang Fatigue Rating Scale (TFRS), the G-8 screening tool, and the symptom diary. This self-administration process is expected to take approximately 10 minutes. If a participant is unable or unwilling to self-report (e.g., due to advanced age or fatigue), the researcher will conduct a structured interview to complete the questionnaires, which is estimated to take 30–40 minutes. Concurrently, all participants will be invited to join the study's official LINE group for communication. Following the collection of baseline questionnaires, a computer-generated randomization sequence will be implemented by personnel not directly involved in the study (i.e., someone other than the principal investigator) to allocate participants to either the experimental group (Group A) or the control group (Group B). Participants in Group A, after confirming their chemotherapy infusion line is properly connected, will begin listening to 30 minutes of self-selected music while concurrently receiving standard care. Participants in Group B will receive standard care only. A total of **60 participants** with Acute Myeloid Leukemia (AML) undergoing chemotherapy are expected to be recruited (n=30 per group). Both groups will be required to complete the symptom diary throughout the 21-day

study period (est. 1 minute per entry). Group A will complete the Fatigue Numerical Rating Scale (NRS) immediately following each music therapy session. Group B will complete the Fatigue NRS 30 minutes after the commencement of their chemotherapy infusion.

On Day 21 (T1), the researcher will collect the post-test data (TFRS, NRS, and G-8) in the ward. If a participant has been discharged, data will be collected via telephone interview or an online questionnaire.

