The laboratory data required for this study (WBC, Hb, Albumin) will be obtained by the researcher through a medical record review. Data from blood samples drawn as part of standard clinical care, taken before chemotherapy (T0) and on Day 21 (± 3 days) (T1), will be utilized. **No additional blood draws will be required for this study.**

Throughout the study period, participants may ask questions at any time via the official LINE group, and the researcher will provide responses.

Ethical Considerations

This study will be initiated only after obtaining approval from the Institutional Review Board (IRB) and securing consent from the nursing administrators and attending physicians of the recruitment site. Prior to formal enrollment, the researcher will personally explain the study's purpose, procedures, and methodology to each potential participant.

The researcher will address all participant inquiries. Participants will be explicitly informed that their participation is voluntary, that they may withdraw from the study at any time without penalty, and that their decision will not affect the quality of their medical treatment or nursing care in any way.

All research data collected from participants will be processed using anonymous coding. The data will be securely stored by the researcher and used exclusively for academic purposes. Confidentiality will be strictly maintained, and data will not be publicly disclosed or used for other purposes, ensuring the protection of participant privacy.

Data Processing and Statistical Analysis

1. Data Management The researcher will review all questionnaires for completeness. All collected data will be coded and entered into the Statistical Packages for the Social Sciences (SPSS) version 26.0 for data processing and management.

2. Statistical Analysis In accordance with the study's objectives, data analysis will be divided into descriptive and inferential statistics, as outlined in Table 3-3.

- **a. Descriptive Statistics:** Based on the characteristics of the variables, data

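### The planned pre/post GEE does not say how the T0 value is used; adjusting the Day 21 comparison for T0 would usually be more precise, by an amount that rests on assumptions

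*Combined protocol and SAP*

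**What the plan says.** In the combined protocol and SAP, Data Processing and Statistical Analysis, b. Inferential Statistics, the inferential plan is that "GEE will be used to compare pre- and post-test values (fatigue severity, Absolute Neutrophil Count [ANC], hemoglobin, and albumin") between the experimental and control groups, on an intention-to-treat basis. GEE is chosen because attrition is expected, "leading to unequal sample sizes at different measurement points". The text gives no model equation, arm-by-time term, working correlation or baseline term. The section points to a Table 3-3 that is not in the available text.

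Under III: Sample Size Calculation, the analysis is to control for "covariates (e.g., age, sex, education level, occupation, perceived economic status, marital status, religious beliefs, and metastasis"). These are examples, and the T0 value of the outcome is not among them.

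On timing, Research Design says "Data will be collected at two main time points: upon admission for initial chemotherapy (Baseline, T0") and Day 21. Table 1 (Schedule of Research Measurements) shows Tang's Fatigue Scale (TFRS), WBC, hemoglobin and albumin at those two times only; the fatigue NRS is also taken on Days 7 and 14. Research Procedures says "Following the collection of baseline questionnaires, a computer-generated randomization sequence will be implemented", and for the laboratory values "Data from blood samples drawn as part of standard clinical care, taken before chemotherapy (T0) and on Day 21". Under Music Therapy Protocol, the music begins with the chemotherapy infusion.

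On size, Research Design plans 44 patients, "with 22 participants allocated to each group", while Research Procedures gives 60 (30 per group). The sample-size section adds "To account for a potential attrition rate of 30" per cent.

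**The concern.** The natural reading of a pre/post GEE by arm is that T0 is one of the responses and the arm effect is the group-by-time term. That model estimates a T0 mean separately in each arm. Yet the T0 questionnaires are completed before randomisation, and the T0 bloods are drawn before chemotherapy, hence before any music. No arm effect can exist at T0. Estimating two T0 means carries their chance difference in full into the arm contrast, whereas adjustment removes only the part that predicts Day 21.

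What is at stake is precision. With 30% loss, 44 recruits leave 44 x 0.7 = 30.8, about 31 patients with a Day 21 value; 60 recruits leave 42. TFRS, named as the primary outcome measure under Research Instruments, is one of the outcomes affected. At this size a loss of precision that can be avoided with data already collected is worth removing.

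**Working it through.** **The plan's own figure.** The plan gives no precision figure for the T0 to Day 21 contrast. Its nearest figure is the required N of 34. A repeated-measures F-test for the within-between interaction with effect size f = 0.21, alpha 0.05, power 0.80, four time points and correlation 0.5 (the last two assumed) returns 34, with power 0.823. With two time points the same formula needs 48. A within-subject test with four times also returns 34, so this figure fixes neither the model nor the correlation.

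**Inputs.** From the documents: 22 or 30 per arm, and 30% attrition, so a fraction p = 0.7 has a Day 21 value. Assumed, because the documents are silent: r between T0 and Day 21 of 0.3, 0.5 or 0.7; Day 21 SD = 1; T0 SD = k; loss at random; no other covariates.

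**Complete pairs, large sample** (variances in units of 2/n, n per arm).
- Pre/post contrast: 1 + k² - 2rk.
- T0-adjusted contrast: 1 - r².
- Difference: (k - r)². The gain is never negative, and it is zero when k = r.
- At k = 1 the relative gain is (1 - r)/2: 35%, 25% and 15% at r = 0.3, 0.5 and 0.7. Simulation with 22 per arm gave 34.0%, 22.4% and 14.2%.

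**With 30% loss, k = 1.** An exchangeable GEE keeps patients who have only T0.
- GEE contrast: (1 - r)² + (1 - r²)/p.
- T0-adjusted: (1 - r²)/p.
- Relative gain: p(1 - r) / [p(1 - r) + (1 + r)].
- r = 0.3: 0.49/1.79 = 27%. r = 0.5: 0.35/1.85 = 19%. r = 0.7: 0.21/1.91 = 11%.

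Estimating the T0 slope multiplies the adjusted variance by about 1 + 1/(completers - 4), that is 28/27 for 31 completers and 39/38 for 42. The gains become 24.7%, 15.9% and 7.7% with 44 recruited, and 25.5%, 16.8% and 8.7% with 60.

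**Simulation with 30% random loss**, exchangeable GEE against T0 adjustment, slope cost included. Ranges cover 44 and 60 recruited and repeated independent runs.

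| SD(T0)/SD(Day 21) | r = 0.3 | r = 0.5 | r = 0.7 |
|---|---|---|---|
| 0.7 | 7 to 10% | 1 to 2% | -2 to 0% |
| 1.0 | 24 to 26% | 16 to 18% | 8 to 10% |
| 1.3 | 41 to 42% | 35 to 38% | 30 to 34% |

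Example cell (44 recruited, k = 1, r = 0.5): standard errors 0.353 and 0.322, and 1 - (0.322/0.353)² = 17%. In that cell, using the unrounded variance ratio 0.836, 44 recruits with T0 adjustment are as precise as 44/0.836 = 52.6 without it. This is one cell, not a general statement.

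**Other working correlation.** The plan names none. Under independence, the GEE contrast at k = 1 has variance 1/p + 1 - 2r, giving large-sample gains of 29%, 25% and 29% at r = 0.3, 0.5 and 0.7. Simulations with slope cost gave about 21-29%. The size therefore depends on the comparator as well as on r and k.

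**The case against.** The strongest reply is that the flaw is inferred. The text does not state a group-by-time term. The covariate list is introduced by examples and covers baseline characteristics, and the table said to outline the analysis is not available. A reader might infer that the plan rules out T0 adjustment; the documents do not support that. What stands is narrower: the available text does not commit to using T0, and its wording suggests a pre/post contrast.

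A second reply is that the size is unknown and could be nil for TFRS. T0 precedes chemotherapy, and the literature review expects fatigue to peak in the week after it, so equal SDs cannot be presumed. This stands, and it is why no single percentage should be quoted without its assumptions.

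Third, the calculations omit the planned covariates. That also stands: with covariates in both models, the relevant r and SDs are those remaining after adjustment.

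Fourth, the N of 34 is matched with four time points, so the sizing may relate to the NRS, which lies outside this point. That is possible. It does not change the argument for the outcomes measured twice.

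Finally, one might prefer a baseline-constrained model to ANCOVA because it keeps patients with T0 only and so seems closer to intention to treat. With one post-baseline time and separate variances, the two give the same arm estimate, and T0-only patients add nothing to it.

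**Conclusion.** The point holds as a matter of precision and as a gap in specification. A reader might infer bias or an invalid test; the documents do not support that, because under randomisation the pre/post contrast estimates the same arm effect.

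For TFRS, hemoglobin, albumin and WBC/ANC, T0 adjustment usually reduces the variance of the arm comparison. With equal SDs the reduction is about 8-26% under 30% random loss against an exchangeable GEE, and 15-35% with complete pairs, for r from 0.7 to 0.3. It runs from about 10% to nil (up to about 2% worse) if T0 is less variable (ratio 0.7), and is about 30-42% if T0 is more variable (ratio 1.3). Every one of these figures rests on assumed SDs and correlations. Random loss is also assumed, although the plan itself names disease progression as a cause of attrition. The change is worth making before analysis. The four-time fatigue NRS is not covered.

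**What to change.** For TFRS, hemoglobin, albumin and WBC/ANC, prespecify the arm effect at Day 21 adjusted for the T0 value of the same outcome. Either of two forms will do, and one is enough:

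- Day 21 ANCOVA on arm and T0, with t-based inference.
- The equivalent baseline-constrained model: one T0 mean for both arms, separate T0 and Day 21 variances, and small-sample-corrected inference.

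If GEE is kept, enter T0 as a covariate for the Day 21 outcome and use a small-sample-corrected variance. Separate variances matter in the constrained form: with an exchangeable correlation instead, it was 4-5% worse than the pre/post contrast at SD ratio 0.7 and r = 0.7. Small-sample inference matters too: in simulation with no true effect and equal SDs, the adjusted test had type I error of 4.9-5.2% with t on completers minus 3 degrees of freedom, but 6.9-8.0% with maximum-likelihood variance and a normal reference.

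The cost is a few lines of SAP text and code, one degree of freedom for the T0 slope, and no new data. The downside is a negligible loss of precision if T0 is much less variable than Day 21 and r is high.
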